Since it has been shown by Foster GD et al. [24] that 86% of overweight and obese diabetic subjects have sleep apnea, we feel that, in addition to including subjects without sleep apnea, we should include patients with sleep apnea controlled on C-PAP. Both of these groups of patients will be protected from any additional hypoxia associated with sleep apnea that would add to the safe hypoxia generated by the tent, but including the group with sleep apnea controlled on C-PAP will allow us to enroll and complete the study which has only enrolled one patient in over a year when limiting those studied to those without sleep apnea.

HYPOTHESIS AND AIMS

Aim: To determine the effect of 2-week overnight sleep in moderate hypoxia on glucose tolerance in participants with type 2 diabetes.

Hypothesis: Exposure to moderate hypoxia (2400 m altitude) for 14 consecutive nights in obese, type 2 diabetic subjects will improve glucose tolerance

Primary endpoint: Results from the 75 g oral glucose tolerance test (OGTT) assessed by different statistical approaches including:

- Traditional area under the curve (glucose and insulin)
- Repeated measures mixed effect model
- Matsuda Index
- Kahn's calculation of indices of insulin sensitivity and insulin secretion

Exploratory endpoints: Fasting plasma fructosamine and hemoglobin A1-C as well as daily body weight

SUBJECTS

We plan to have n = 10 completers.

Inclusion criteria:

- Aged 20-65 yrs
- Have a BMI < 55 kg/m²
- Body weight 450 lbs or less

PBRC# 2015-018

- Have *either* been diagnosed with type 2 diabetes, or 125 mg/dl < Fasting Blood Sugar < 200 mg/dl, or hemoglobin A1-C \geq 6.5%
- Non-smokers
- Weight stable over the previous 3 months (< 3 kg fluctuation)
- Known diagnosis of sleep apnea and ownership of a continuous positive airway pressure (C-PAP) device that must be worn throughout the nights spent in the tent
- If no known presence of sleep apnea, be willing to spend one night in a sleep laboratory (Louisiana Sleep Foundation) to assess presence of sleep apnea

Exclusion criteria:

- Diagnosed with T2DM \geq 15 years ago
- Pregnant Women
- Current insulin treatment
- Treatment with sulfonylureas or glitinides
- Treatment with a GLP-1 agonist
- Any other diabetes medication other than an oral agent is exclusionary unless otherwise cleared by medical investigator.
- Chronic Obstructive Pulmonary Disease (COPD)
- Congestive heart failure

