Participants will report to the PBRC clinic after a >10-h overnight fast. The screening visit includes an explanation of the purpose of the study, a description of the procedures and the reading and signing of informed consent. Volunteers will then complete a brief personal and family medical history. Height, weight, waist and hip circumference, vital signs (blood pressure, pulse, oral temperature) will be measured. Volunteers will then have an EKG. Subjects with a previous sleep apnea diagnosis must possess a C-PAP device and must agree to use the CPAP device during the nights spent in the tent; if no C-PAP device is available for usage, the subject will not be eligible to participate in the study. If subjects are considered to be eligible up to this point, blood will be drawn for a complete blood count, blood chemistry (Chem15), and a hemoglobin A1-C as part of the draw. Subjects who do not meet the eligibility criteria will be immediately informed in person or by phone. An interview with a trained psychologist will identify potential barriers to enrollment into the SLEEPDIABETES study and also barriers to have the hypoxia tent system setup at the participant's home. Only subjects without a previous sleep apnea diagnosis and who meet all eligibility criteria will next undergo a two-step process to: (1) confirm the absence of sleep apnea (home sleep test, or HST), as well as (2) confirm these subjects without a sleep apnea diagnosis exhibit safe oxygen saturation levels (monitored sleeping study at the Louisiana Sleep Foundation, a certified sleep laboratory) while sleeping under the mild hypoxic conditions denoted by the study. Subjects previously diagnosed with sleep apnea and who possess a C-PAP device will not undergo testing at the Louisiana Sleep Foundation.

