(1) Home Sleep Test (HST): Subjects without a sleep apnea diagnosis will first undergo a home sleep test conducted by the Louisiana Sleep Foundation under the direction of [name], MD, DABSM, the chief medical director of the Foundation. Subjects will obtain the home sleep test from [name] and will be given instructions on how to wear the device during a single night of sleep. The device will record breathing rates and oxygen saturation levels throughout the single night of sleep. After the single night sleep, subjects will be instructed to return the device to the Louisiana Sleep Foundation where [name] will review the sleep data and identify the potential presence of sleep apnea. If the presence of sleep apnea is detected, subjects will be immediately informed of their ineligibility to participate in the study. If a negative test for sleep apnea is concluded, subjects will next undergo a monitored sleep study.

(2) Monitored Sleep Study: Subjects who have a negative test for sleep apnea following a HST will next undergo a monitored night of sleep under hypoxic conditions at the Louisiana Sleep Foundation. Subjects will arrive at the Louisiana Sleep Foundation on the evening of their monitored sleep study. A sleep technician will closely monitor the subject's oxyhemoglobin saturation throughout a single night of sleep under hypoxic conditions (2400 m altitude). Hypoxic conditions will be achieved via a hypoxic tent, as previously described and conducted at Pennington Biomedical Research Center [20]. Following the technician-monitored night of sleep, [name] will review the sleep data and provide insight as to the subject's ability to participate in the study given expected oxyhemoglobin saturation levels at 2400 m. Subjects

who exhibit <78% oxyhemoglobin saturations, or who display sleep data of safety concern to [name], will be informed of their ineligibility to participate in the study.

If the HST and sleep center monitoring are within safe ranges for study participation following evaluation by [name], the participant will officially be accepted into the study and will begin baseline testing (Day 0) within weeks and in agreement with schedules. All subjects who have a known sleep apnea diagnosis, possess a C-PAP device, and are agreeable to using the C-PAP device during the nights spent in the tent will be accepted into the study as well.

EXPERIMENTAL DESIGN

This study includes outpatient and in-home visits and will consist of three periods:

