- 1) **Baseline** measures of glucose tolerance (OGTT) and body composition (DXA)
- 2) **Intervention** involving 14 night stays in simulated altitude (hypoxic tent in home)
- 3) **Post-treatment** (after 14 nights in hypoxia) measures of glucose tolerance

After screening, subjects will be asked to maintain their usual diet and physical activity levels.

Baseline:

A 75-g OGTT will be performed. Body composition will be measured by DXA. Fasting plasma fructosamine will also be collected via blood draw. A urine pregnancy test will be performed on all females of child-bearing potential prior to the DXA.

Intervention: Nightly exposure to hypoxia

Over the following 14 nights, participants will sleep under a tent simulating an altitude of 2400m (~7500 ft) for 7-12 hrs each night depending on their usual sleep pattern in their bedroom. Each participant will be informed that their partner or household member, or any other individuals, are prohibited from entering or sleeping in the tent.

Post treatment measurements:

After the 7th night of hypoxic sleep, participants will come to the Pennington Biomedical clinic to provide a fasting blood sample to measure glucose and insulin. We will also collect information of the quality of their sleep under the hypoxic tent.

The morning of the 14th exposure to hypoxia, participants will come to the Pennington Biomedical clinic facilities in a fasting state to perform a post intervention assessment.

Approximately 15 min after arrival, a 75-g OGTT will be performed. Fasting plasma fructosamine and hemoglobin A1-C will also be collected via blood draw.

Table 1. Schedule of Procedures

	Screening	Sleep Screening (HST & Sleep Study)	Baseline (Day 0)	Mid-Intervention (Day 7)	Post-Intervention (Day 14)
Health questionnaire	X				
Body weight	X		X	X	X
Vital signs*	X				
Electrocardiogram	X				
Blood draw	X		X	X	X
Oral glucose tolerance test			X		X
Body composition by DXA			X		
Urinalysis	X				
Urine Pregnancy Test			X		
Oxyhemoglobin saturation**		X			

* blood pressure, pulse, oral temperature

** Only performed on subjects without previous sleep apnea diagnosis. Time between screening and sleep screening, as well as sleep screening and baseline testing (Day 0), will vary depending on scheduling at Pennington Biomedical and the Louisiana Sleep Foundation.

METHODS AND PROCEDURES

Urine and blood.

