Eligible subjects without a previous sleep apnea diagnosis will undergo an extensive two-step sleep evaluation, involving a home sleep test as well as a monitored sleep test at the Louisiana Sleep Foundation, to identify the presence of sleep apnea as well as closely monitor and evaluate oxyhemoglobin saturation levels during a single night sleep at 2400 m in the hypoxic tent, respectively. Sleep data will be thoroughly evaluated and assessed on a subject-by-subject basis by the chief medical director of the Louisiana Sleep Foundation to ensure the upmost safety precautions are taken. Only those subjects who exemplify safe oxyhemoglobin saturation levels during both sleep evaluation tests will be allowed to enroll in the study.

Eligible subjects with previous sleep apnea diagnosis who possess a C-PAP device will be required to use the C-PAP device throughout the nights spent in the tent.

Adverse Event Reporting: Adverse event monitoring will occur at mid-intervention (Day 7) and post-intervention (Day 14) visits, and participants will be instructed to call the study coordinator ([name]) at the onset of any abnormal effects (headache, nausea, vomiting, dizziness) between visits.

Data Safety Monitoring Plan. Drs. [name] and [name] will be responsible for monitoring the data, assuring protocol compliance, and conducting safety reviews after completion of the first participants and then every 6 weeks. During the entire study, [name] will monitor adverse events and determine if they are attributed to the study procedures. If any of those adverse events are suspected to be related to study procedures, they will be immediately reported to the PI and the IRB.

Such study has already been conducted in 8 participants with obesity and identified a 20% improvement in insulin sensitivity.

Potential Benefits: There is no direct benefit to the volunteers but knowledge may be gained that will benefit others. Participants will, however, receive some information about their health.

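### The only scheduled pregnancy test is on Day 0, so on the pathway without a prior sleep apnea diagnosis one hypoxic night comes before it

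*Combined protocol and SAP*

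**What the plan says.** The exclusion criteria under SUBJECTS list "Pregnant Women" without condition, and do not say how or when this is verified. The Baseline paragraph of EXPERIMENTAL DESIGN gives the only test: "A urine pregnancy test will be performed on all females of child-bearing potential prior to the DXA". Table 1 marks it once, under Day 0.

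SCREENING describes the route for people without a prior sleep apnea diagnosis. Those who meet the eligibility criteria go on to a home sleep test, and then: "Subjects who have a negative test for sleep apnea following a HST will next undergo a monitored night of sleep under hypoxic conditions". RISK/BENEFIT ASSESSMENT (Minimizing Risks) gives the purpose of that second step, which is to "evaluate oxyhemoglobin saturation levels during a single night sleep at 2400 m in the hypoxic tent". Acceptance comes only after these data have been reviewed: "the participant will officially be accepted into the study and will begin baseline testing (Day 0) within weeks". The Table 1 footnote adds that the intervals between screening, sleep screening and Day 0 will vary with scheduling.

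The other route has no such night: "Subjects previously diagnosed with sleep apnea and who possess a C-PAP device will not undergo testing at the Louisiana Sleep Foundation".

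**The concern.** An exclusion that covers the whole study would normally be confirmed before the first study exposure. Here the test is placed by reference to the scan. The tent is the study intervention, and one group of participants meets it before Day 0, at the same simulated altitude as the home nights.

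The protocol does not rely on a woman's own report before a DXA whose stated dose is under 1 mrem; it asks for a urine test. It schedules no test before the first night in the tent. The risk statement for sleeping under hypoxia rests on C-PAP use and on the sleep-test exclusions, and does not mention pregnancy.

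What is at stake is participant protection: a pregnancy nobody yet knows of could reach the first hypoxic exposure untested. No estimate or test of the OGTT endpoints is involved.

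**Working it through.** No formula applies and the plan gives no figure to reproduce. The check is of the order of procedures.

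**1. Count the scheduled tests.** The pregnancy-test row of Table 1 reads Screening 0, Sleep Screening 0, Day 0 1, Day 7 0, Day 14 0. The total is 0 + 0 + 1 + 0 + 0 = 1 mark in 5 columns, with none in the 2 columns before Day 0. The Baseline text says the same, so the result does not depend on the table layout.

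**2. Look for an earlier item that could do the same job.**
- The phone-screen topics listed under RECRUITMENT do not name pregnancy.
- Urine and blood (METHODS AND PROCEDURES) assigns the screening blood to CBC, Chem15 and hemoglobin A1-C, and the screening urine to urinalysis.
- At the screening visit, "Volunteers will then complete a brief personal and family medical history", and Table 1 lists a health questionnaire. Either may bring out a known pregnancy. Their content is not shown, and neither can detect one the woman is unaware of.

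**3. Place the nights at 2400 m around the test.**

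| Step, in order | No prior diagnosis, negative home sleep test | Prior diagnosis, owns C-PAP |
|---|---|---|
| Screening visit | history and questionnaire, no pregnancy test | the same |
| Home sleep test | one night, not described as hypoxic | not done |
| Monitored sleep study | 1 night at 2400 m | not done |
| Day 0 | pregnancy test, then DXA | the same |
| Home intervention | 14 nights at 2400 m | 14 nights at 2400 m |
| **Nights before / after the test** | **1 / 14** | **0 / 14** |

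RISK/BENEFIT ASSESSMENT confirms that the monitored night comes before enrolment on the first pathway: "Only those subjects who exemplify safe oxyhemoglobin saturation levels during both sleep evaluation tests will be allowed to enroll in the study".

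**4. Ask how many women this touches.** This cannot be derived, because the documents do not give the number of women of child-bearing potential on the first pathway. It is probably very small: 10 completers are planned over both pathways, and the background reports one enrolment in over a year when the study was limited to people without sleep apnea. That figure counts enrolments, not monitored nights, so it is a guide and not a bound.

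**The case against.** The strongest reply is that SCREENING sends only people who meet all the eligibility criteria to the sleep tests, so pregnancy has already been excluded by then. As a statement of intent, this stands. A reader might argue that the phrase cannot cover pregnancy, because the sleep-test exclusions are decided later. That does not follow: only the sleep criteria need be deferred, and the natural reading is that all others have been applied. What remains is that no test is scheduled to confirm this one.

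A second reply is that the text is consistent. The exclusion does not say that a test must verify it, and other exclusions, such as COPD or past altitude sickness, have no dedicated test at screening either. The test sits before the one procedure whose risk text mentions pregnancy. This also stands. A reader might infer that the sections contradict each other, but the documents show only an order that leaves a gap.

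Third, the documents do not say why pregnant women are excluded. They liken 2400 m to mountain resorts and Mexico City and attach the FDA's nonsignificant-risk determination. Neither addresses pregnancy, so neither settles the matter. But a reader who infers a known harm to a pregnancy from one night in the tent goes beyond what is written.

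Finally, it is a single night with a technician present. That is true and limits the size of the point, although what the technician watches is oxygen saturation, not eligibility.

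**Conclusion.** The point holds as a minor one, worth acting on because the remedy is cheap. On one of the two pathways, the first study exposure to hypoxia comes before the only test that could detect an unrecognised pregnancy. The exposure concerned is one monitored night. The 14-night intervention is preceded by the test on both pathways, and sample size, endpoints and analysis are untouched.

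A reader might infer that the plan lets women known to be pregnant into the tent, or that the home intervention starts untested. The documents support neither.

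The conclusion assumes that visits follow the written order, and that history and questionnaire can reveal at most a known pregnancy. The absence of an earlier scheduled test is clear from text and table. How the exclusion is otherwise ascertained is less certain, because the consent pages were not available for this review and may say more. Nothing is claimed about women with a positive home sleep test, since the exclusion criteria and SCREENING differ on whether they can take part.

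**What to change.** Amend the screening text and Table 1 so that the urine pregnancy test already in the protocol is also done, for women of child-bearing potential, before the monitored hypoxic night. Keep the Day 0 test before the DXA; it covers the variable interval after that night.

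The investigators should choose the visit and state it:
- **Urine already collected at screening.** No new sample is needed, but the interval up to the monitored night is left uncovered, and some strips are used on women who later fail the home sleep test.
- **A test at the sleep-screening visit.** This covers that interval. It needs a urine sample at the sleep laboratory, a brief instruction to staff and a stated way of handling a positive result.

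Either way the cost is one strip per woman tested, one further mark in Table 1 and one sentence of text. No exposure, treatment or stopping rule changes.

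### Blood pressure and pulse are scheduled at Screening only, so there is no Day 0 reference and no reading after tent exposure starts, although participants attend the clinic on Day 0, Day 7 and Day 14

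*Combined protocol and SAP*

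**What the plan says.** In Table 1 (Experimental Design), the vital signs row has a single mark, under Screening, and its footnote reads "blood pressure, pulse, oral temperature". The Screening section agrees: "Height, weight, waist and hip circumference, vital signs (blood pressure, pulse, oral temperature) will be measured". The Vital signs paragraph under Methods and Procedures says how the readings are taken (lying down, with pulse counted over 60 seconds) but names no visit.

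Participants return three times. Day 0 has the baseline OGTT, DXA and blood draw. After the seventh night, "participants will come to the Pennington Biomedical clinic to provide a fasting blood sample to measure glucose and insulin". On Day 14 they return fasting: "Approximately 15 min after arrival, a 75-g OGTT will be performed". Body weight and blood draws are scheduled at all of these visits; blood pressure and pulse are not.

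The Risk/Benefit Assessment sets out the safety follow-up:
- questions about altitude symptoms
- adverse event checks on Day 7 and Day 14
- an instruction to call the coordinator if abnormal effects begin between visits
- prompt reporting of suspected related events to the PI and IRB
- withdrawal for acute altitude sickness or any serious adverse event
- safety reviews after the first participants finish and every 6 weeks after that.

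**The concern.** Every safeguard that operates during exposure starts from a symptom or a reported event. A rise in blood pressure or pulse need not cause symptoms. A large one present at the Day 7 visit could therefore go unseen, with half the tent nights still to come. The eligibility lists contain no blood pressure limit, so entry criteria do not narrow the starting range.

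The pilot would also finish with no blood pressure or pulse data after exposure to report beside its adverse events. The protocol presents the tent as a potential home treatment for diabetes, so that is basic safety information it could collect at almost no cost.

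**Working it through.** **Is the gap real, or a fault in the extracted table?** The body weight and blood draw rows each show marks at Screening, Day 0, Day 7 and Day 14, and the OGTT row at Day 0 and Day 14. Column positions therefore survived, and the blanks in the vital signs row are genuine. The Baseline and Post treatment text lists no vital signs either. The two sleep-screening steps record breathing rate and oxygen saturation; neither names blood pressure or pulse.

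**Count from Table 1.**

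| Visit | Clinic attendance | Blood pressure and pulse |
|---|---|---|
| Screening | yes | yes |
| Day 0 | yes | no |
| Day 7 | yes | no |
| Day 14 | yes | no |

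That is 1 of 4 clinic visits, and 0 of 2 after exposure starts. With the planned 10 completers, marking the three empty visits adds 10 readings at each. The three sets do different work. Day 0 is the reference. Day 7 is the only set that can protect anyone during exposure. Day 14 comes after the exposure period and serves description only.

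**Exposure left at Day 7.** Nights are 7-12 hours. Total: 14 x 7 = 98 h to 14 x 12 = 168 h. After Day 7: 7 x 7 = 49 h to 7 x 12 = 84 h, or half.

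**What one Day 7 systolic reading can show.** The documents give no variability for blood pressure and no action limit. Assume a normally distributed within-person change with an SD of 8, 10 or 12 mmHg and, for illustration only, a flag at a rise of more than 20 mmHg from Day 0. The probability of a flag is P(Z > (20 - true rise)/SD).

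| True rise | SD 8 | SD 10 | SD 12 |
|---|---|---|---|
| 0 mmHg | 0.6% | 2.3% | 4.8% |
| 10 mmHg | 10.6% | 15.9% | 20.2% |
| 30 mmHg | 89.4% | 84.1% | 79.8% |

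With no true change, the expected number of false flags among 10 participants is 10 x 0.0062 = 0.06, 10 x 0.0228 = 0.23 and 10 x 0.0478 = 0.48. The chance of at least one, 1 - (1 - p)^10, is 6%, 21% and 39%. Adding a pulse limit would raise these figures.

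**Group summary.** The 95% half-width of a mean change at n = 10 is 2.262 x SD / sqrt(10) = 5.7, 7.2 and 8.6 mmHg. That is enough for a description, not for a claim about a small shift.

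So a single reading picks up large individual changes reasonably well and small ones poorly.

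**The case against.** The strongest case against is that this is a preference and not a defect. Blood pressure and pulse are not endpoints, and the glucose comparison does not use them. The hazards the protocol names are extra hypoxia from sleep apnea and altitude sickness, and an awake reading in the clinic measures neither. COPD, heart failure and prior stroke or infarction are excluded, and FDA classed the study as non-significant risk. All of this stands and limits the weight of the point. It does not remove the gap, because none of these measures shows a change without symptoms in a participant who is already in the clinic.

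Two further objections stand in part. A Screening value exists, so what is missing is a Day 0 reference, not every reading before exposure. For those who go through sleep testing, "Time between screening and sleep screening, as well as sleep screening and baseline testing (Day 0), will vary depending on scheduling", but the protocol expects baseline testing within weeks, so Screening is an imperfect reference and not a useless one. Also, flagging a reading protects nobody unless a confirmed change leads to a decision; the fix below supplies one.

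A reader might infer that safety during exposure is unmonitored because scheduled reviews are 42 days apart (6 x 7) against a 14-night exposure. The documents do not support that. Adverse events are followed throughout, participants can call in, and there are withdrawal rules.

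A reader might also infer that this change answers the question about participants on C-PAP. "Subjects previously diagnosed with sleep apnea and who possess a C-PAP device will not undergo testing at the Louisiana Sleep Foundation", and the footnote to the saturation row says "Only performed on subjects without previous sleep apnea diagnosis". They therefore have no planned saturation reading at 2400 m. They may be much of the sample, since the protocol describes a study "which has only enrolled one patient in over a year when limiting those studied to those without sleep apnea", but no count is given. That gap is separate, and clinic blood pressure does not close it.

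**Conclusion.** The point holds as an optional, low-cost safety improvement. Blood pressure and pulse are planned at Screening only, with no Day 0 reference and none at either visit after exposure starts. The practical gain is one protective reading per participant, at Day 7 with 7 of 14 nights left, plus a descriptive record at Day 14.

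The schedule finding needs no assumptions. The flag rates rest on the assumed SD of 8-12 mmHg, normality and the illustrative 20 mmHg limit; none of these comes from the documents.

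It would go too far to read this as evidence that the tent raises blood pressure or pulse. The documents contain no such evidence. Awake readings outside the tent do not show how participants tolerate the night, and without a control arm a mean shift could not be attributed to hypoxia. The glucose tolerance results are unaffected.

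**What to change.** In Table 1, mark blood pressure and pulse at Day 0, Day 7 and Day 14, taken lying down by the method already in the Vital signs paragraph and before the blood draw or placement of the OGTT line.

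In the Adverse Event Reporting paragraph, add that the medical investigator reviews the Day 7 values against the participant's own Day 0 values before the next tent night. Write down in advance the change that prompts a repeat reading. If the repeat confirms it, the medical investigator decides whether the participant continues, pauses or withdraws. The limit is for the medical investigator to choose; the 20 mmHg used above is only an illustration.

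Summarise changes from Day 0 descriptively beside the adverse events, with no significance test, and state that these are awake readings outside the tent in an uncontrolled study.

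The cost is a few minutes at three visits already scheduled. The pulse is a 60-second count, and on Day 14 about 15 minutes already lie between arrival and the OGTT. No extra blood is needed. False flags will prompt an occasional repeat: 0.06-0.48 expected per 10 participants at Day 7 for systolic pressure under the assumptions above, and more once pulse is included.
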